5 COMPLICATIONS

In addition to the standard operating procedures for reporting complications per hospital/physician protocol, all clinical events, including both observed or volunteered problems, complaints, symptoms, physical signs or disease which either occur during the study, having been absent at baseline, or, if present at baseline, appear to worsen during the clinical outcomes collection study are to be recorded as complications in the subject's medical record and on the appropriate case report form. In addition for any cleared device, a Product Experience Report (PER) must be completed per the manufacturer's customary complaint procedure (SOP 114.0.1 – Product Complaint Procedure).

5.1 Definition

A complication is any written, electronic, or oral communication that alleges deficiencies related to the identity, quality, durability, reliability, safety, effectiveness, performance, or any indication of the failure of a device to meet a user or customer's expectations. The complaint may be the possible failure of a device, labeling, or packaging to meet any of its specifications after it is released for distribution.

6 Primary Objective and Sample Size Justification

The primary objective of this study is to obtain a precise estimate of the proportion of patients who have moderate-to-severe adjacent-level ossification at 24 months, indicated by a severity of Grade 1, 2, or 3 at any level on the 24-month lateral radiograph. A point estimate and two-sided, 95% confidence interval for this endpoint will be calculated using the normal approximation to the binomial, as follows:

$$\hat{p} \pm z_{1-\frac{\alpha}{2}} \sqrt{\frac{\hat{p}(1-\hat{p})}{n}}$$

Where:

\hat{p} = the proportion of soft tissue masses found

n = the total number of patients

α = 0.05

The sample size for this study was based on the number of patients needed in order to calculate, within a precision of 10%, a 95% confidence interval for the proportion of patients with moderate-to-severe adjacent-level ossification. The “precision” of a confidence interval refers to the distance from the estimated proportion (point estimate) to the upper and lower limits of the confidence interval. The full width of the confidence interval is twice the precision. This sample size assumes that the rate of incidence will be approximately what was observed in a study conducted by Park, et.al². This study indicates that rate of incidence of moderate-to-severe adjacent-level ossification observed in this study for patients with a PDD of > 5mm is 45.5%. Under this assumption, a sample size of 96 patients will allow a precision of 10% to be achieved. Accounting for possible attrition of up to 15% gives a sample size of 113 patients.

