2 PRODUCT DESCRIPTION

Device Name: MaxAn[®] Anterior Cervical Plate System

The MaxAn[®] Anterior Cervical Plate System provides a simple, efficient and innovative approach to anterior cervical plating. The system offers a decompression-based technique for cervical spine stabilization and introduces an innovative one-level plate technique that provides a direct relationship between the bone graft/spacer size and the position of the plate holes. The unique ability to obtain maximum screw angulation and place a fixed screw at any angle up to 30° cephalad on the superior end of the plate and up to 30°caudal on the inferior end of the plate allows for versatile screw placement close to the endplates. Note that the screws converge at 10° in the transverse plane and are not intended to have additional variability in that plane. The significant cephalad-caudal angulation affords the surgeon the opportunity to choose a smaller plate to help minimize the potential for adjacent level ossification.

The plate is low profile and allows for excellent intra-operative visualization of the vertebral end plate and graft. The system also provides a choice of fixed and variable self-drilling screws to provide the surgeon with multiple options.

The MaxAn[®] Anterior Cervical Plate System is an anterior cervical spinal fixation device made from titanium alloy (Ti-6Al-4VELI). Pre-contoured plates that conform to the natural lordotic curvature of the spine are available in one, two, or three level configurations. These offerings also range from 8.0mm to 72mm in length when measured from screw hole to screw hole. The system includes variable and fixed bone screws, which are available in 4.0mm and 4.5mm diameters in various lengths. The MaxAn[®] Anterior Cervical Plate System is cleared under K080646.

Indications For Use: The MaxAn[®] Anterior Cervical Plate System is intended for anterior interbody screw fixation of the cervical spine. The system is indicated for use in the temporary stabilization of the anterior spine during the development of cervical spinal fusions in patients with degenerative disc disease (as defined by neck pain of discogenic origin confirmed by patient history and radiographic studies), trauma (including fractures), tumors, deformity (defined as 'kyphosis, lordosis, or scoliosis), pseudarthrosis, and/or failed previous fusions. The intended levels for treatment range from C2 -T1.

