Screws will be locked and tightened per the MaxAn System ring locking mechanism and closure will be performed per the surgeon's normal preference in an ACDF. Data will be collected during and immediately after the surgery according to the parameters described by the MaxAn[®] Anterior Cervical Plate CRFs. This includes: duration of surgery, blood loss, OR time, length of hospital stay, instrumentation used, type of procedure, surgical level, biological augmentation, type of implants and any interbody fixation system used (if applicable). In addition, all intra-operative complications (e.g. excessive blood loss, hematoma, vascular injury, etc.) will be reported and recorded as a complication on the CRF.

Intra-operative (after hardware is completed) or immediate post-operative x-rays need to be obtained at this time point. These images will be provided to Biomet to review along with the data collected from the surgical visit. We will be assessing the position of the plate at this time point at both the plate level and the distance to the adjacent level. Postoperative care will follow the standard of care at each institution for subjects who undergo anterior cervical fusion procedures.

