APPENDIX 1: Data Collection Forms

The designated protocol visits occur pre-operatively, intra- and post-operatively and 3-months post-operatively.

Informed Consent Form – Signed by subject at pre-op visit.
Demographics & Physical Exam – Completed by STAFF, information found in Medical History. This form is completed only once.
Medical History - Completed by STAFF, information found in Medical History. This form is completed only once.
Previous Spine Surgery History - Completed by STAFF. This form is completed only once.
Non-Operative Treatment - Completed by STAFF. This form is completed only once.
Current Surgery - Completed by STAFF, information taken from Operative Notes and Discharge Report. This form is completed only once after the subject has had surgery.
Post Market Follow-Up Survey – to be completed by operating SURGEON at the 6, 12 and 24 month follow-up visits.
Neck Disability Index Form – To be completed by the subject at the pre-operative and 6, 12 and 24 month follow-up visits.
SF-36 Health Survey – To be completed by the subject at the pre-operative and 6, 12 and 24 month follow-up visits.
Neck and Shoulder/Arm Pain VAS – To be completed by the subject at the pre-operative and 6, 12 and 24 month follow-up visits.
Medication Log - Completed by STAFF. This form is completed and updated pre-operatively, intra-operatively, post-operatively, and at the 6, 12 and 24-month follow-up visits.
Complications Form - Completed by STAFF or SURGEON only if this occurs.

BTBS.CR.SP.009.11v1

MaxAn[®] Cervical Post Market Surveillance

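### Section 5.1 defines a complication as a product complaint, contradicting the clinical recording rules in Sections 5 and 4.2, so complication data could differ between sites

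*Combined protocol and SAP*

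**What the plan says.** Section 5 gives a broad clinical rule. It covers "all clinical events, including both observed or volunteered problems, complaints, symptoms, physical signs or disease which either occur during the study" (or, if present at baseline, that worsen), and these "are to be recorded as complications in the subject's medical record and on the appropriate case report form". It then adds a separate route for product matters: "In addition for any cleared device, a Product Experience Report (PER) must be completed per the manufacturer's customary complaint procedure". The plate system falls under that route, since Section 2 states that it "Anterior Cervical Plate System is cleared under K080646".

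Section 5.1, headed Definition, follows directly and says something else: "A complication is any written, electronic, or oral communication that alleges deficiencies related to the identity, quality, durability, reliability, safety, effectiveness, performance". Its next sentence changes the noun: "The complaint may be the possible failure of a device, labeling, or packaging to meet any of its specifications".

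Section 4.2 uses the word in the clinical sense and carries its own recording instruction: "all intra-operative complications (e.g. excessive blood loss, hematoma, vascular injury, etc.) will be reported and recorded as a complication on the CRF".

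Appendix 1 is the only place that names the form: "Complications Form - Completed by STAFF or SURGEON only if this occurs". It does not say which meaning of complication is the trigger.

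**The concern.** A complication under Section 5 is something that happens to a patient. Under Section 5.1 it is a statement that someone makes about a product. These are different things, and the second carries the heading Definition. Nothing in 5.1 says that it supplements Section 5 or applies only to the Product Experience Report.

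Section 1 gives the study's purpose as documenting device performance and clinical outcomes, and complications belong to those outcomes. Section 3 allows up to 15 centers. The Complications Form is filled in only when a complication occurs, so its content depends on what staff take the word to mean. If sites differ, a blank form could mean either that no clinical event occurred or that nobody alleged a device deficiency. A completed form could describe a packaging complaint. Counts pooled over such sites would not have one meaning.

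**Working it through.** **Figures in the plan.** Section 6 gives the only sample-size figures. They rest on an ossification proportion of 45.5%, a half-width of 10% and a two-sided 95% interval:

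- n = z² p(1 − p) / d² = 1.96² × 0.455 × 0.545 / 0.10² = 95.3, rounded up to 96.
- With 15% attrition: 96 / 0.85 = 112.9, rounded up to 113.

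Both stated figures reproduce. No complication rate enters either formula, so the definition of a complication cannot affect them. The primary endpoint is graded from the 24-month lateral radiograph and does not use the Complications Form.

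**The two meanings applied to the same cases.**

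| Case | Complication under Sections 5 or 4.2? | Complication under Section 5.1? |
|---|---|---|
| Intra-operative hematoma, no device deficiency alleged | Yes (both sections) | No |
| New symptom after discharge, no device deficiency alleged | Yes (Section 5) | No |
| Labeling or packaging complaint, no clinical event | No | Yes |
| New clinical event with an alleged device failure | Yes | Yes |

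The definitions agree only in the last row. Neither contains the other, so the mismatch can add records as well as remove them.

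**Which meaning is intended.** Uses of complication or complications in running text, leaving out the Section 5 heading and the name of the form:

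- Section 4.2: 2, both clinical.
- Section 5: 2, both clinical.
- Section 5.1: 1, in complaint terms.

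That is 2 + 2 = 4 clinical uses out of 5. The second sentence of 5.1 speaks of a complaint, and Section 5 already sends complaints to the Product Experience Report. The 5.1 text therefore reads as the definition of a product complaint placed under the wrong word. The count bears on intention only; it does not measure an effect.

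**Whether another section settles it.**

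- Section 4.3 has the investigator assess adverse events related to the procedure or the device at 6, 12 and 24 months. This captures events independently of the word complication, but it is narrower than Section 5 and does not define the word.
- The Reports section (numbered 6.2, within Section 7) requires reports of unanticipated adverse device effects, a narrower class again.
- Section 7.8 checks CRFs against source, and Section 7.8.1 reviews incoming data for adverse events. Neither says which definition makes a record complete.
- Appendix 1 cites no section as the trigger for the form.

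None of these corrects 5.1 or says which meaning governs the form.

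**The case against.** The strongest reply is that Section 5 is mandatory and complete in itself. It does not refer to complications as defined in 5.1; it says directly that clinical events are recorded as complications, and on a CRF. Appendix 1 lists one form with the matching name, so most readers would connect the two. A site that left clinical events out would have to disregard the instruction printed immediately above 5.1. Section 4.2 binds intra-operative events to the CRF in clinical terms whatever 5.1 says. The visit-level assessment in Section 4.3 and the device-effect reports are further routes. Appendix 1 also lists a surgeon-completed follow-up survey at each visit, although its content is not shown.

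Much of this stands. A reader might infer that clinical complications will be widely lost, or that Section 5 is the only instruction to record them. The documents support neither reading: Section 4.2 is a second recording instruction, and the other routes make large-scale omission unlikely. An intra-operative hematoma, for example, must be recorded under Section 4.2 in any case.

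The reply does not remove the contradiction. The link from Section 5 to the form is implied, whereas the formal definition that cuts against it is explicit. Nor does the reply deal with the opposite error, in which product complaints without any clinical event are logged as complications.

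It is also fair to say that the Complications Form and the complaint procedure are not reproduced and might resolve the matter. That cannot be judged from the documents.

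**Conclusion.** The contradiction is plain on the page and should be corrected. Section 5.1 is wrong as a definition of what Sections 5 and 4.2 call a complication. The consequence is limited: complication data could be inconsistent between sites, with some complaints wrongly included and some clinical events arguably outside the formal definition.

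The size cannot be given, because the documents state no expected complication rate or count. No complication table is named either; Section 4.5 promises only tables and descriptive statistics for outcomes, so the effect falls on whatever complication data are reported. A reader might infer that the primary estimate or the sample size is at risk; as shown above, neither depends on this definition.

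The conclusion assumes that Sections 5 and 4.2 express the intended meaning, which the wording supports but no section states. It also assumes that the unseen form and complaint procedure do not already settle the point.

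**What to change.** 1. Make the Section 5 wording the single definition of a complication.
2. Retitle the present 5.1 text as Product complaint and tie it expressly to the Product Experience Report.
3. State in Appendix 1 that the Section 5 definition triggers the Complications Form.
4. Keep product complaints out of any complication counts that are reported.

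The cost is a small wording amendment to Section 5.1 and Appendix 1, handled through the amendment route in Section 7.3. How far the number of recorded events would change cannot be estimated from the documents. Whether the form itself needs editing cannot be judged without seeing it.

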1 STUDY PURPOSE

The purpose of this Post Market Surveillance Validation is to document the performance and clinical outcomes of the MaxAn[®] Anterior Cervical Plate System. [name], et.al conducted a retrospective review and found a positive association between adjacent-level ossification following anterior cervical plate procedures and the plate-to-disc distance.¹ They concluded that when the anterior cervical plates were placed at least 5mm away from the adjacent disc spaces, there was a decrease in the likelihood of moderate-to-severe adjacent-level ossification. The design of the MaxAn Anterior Cervical Plate and accompanying technique allows this type of plate placement; therefore we will be looking at the radiographic outcomes of these subjects and comparing them to the retrospective chart review conducted by [name]. Using the MaxAn Technique allows you to achieve plate placement of 5mm from the supraadjacent level which will help minimize the risk of adjacent level ossification.

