4.4.5 Adjacent Level Ossification

The severity of adjacent level ossification will be measure on the last follow-up (24 month) lateral radiograph as:

- Grade 0 – None
- Grade 1 – Mild (if the ossification extended across <50% of the disc space)
- Grade 2 – Moderate (if the ossification extended across \geq 50% of the disc space)
- Grade 3 – Severe (if there is complete bridging of the adjacent disc space)

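### The primary endpoint is named moderate-to-severe ossification but counts Grade 1, which the protocol's own scale calls mild

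*Combined protocol and SAP*

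**What the plan says.** Section 6 (Primary Objective and Sample Size Justification) makes the target the proportion of patients with "moderate-to-severe adjacent-level ossification at 24 months, indicated by a severity of Grade 1, 2, or 3 at any level", read on the lateral film at that visit.

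Section 4.4.5 (Adjacent Level Ossification) gives the scale. Grade 0 is none. The next step is "Grade 1 – Mild (if the ossification extended across <50% of the disc space", then "Grade 2 – Moderate" for half the disc space or more. Grade 3 is severe, meaning complete bridging.

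Section 6 takes its planning rate from a cited study and describes it in the same terms as the label: "rate of incidence of moderate-to-severe adjacent-level ossification observed in this study for patients with a PDD of > 5mm is 45.5" per cent. Section 1 (Study Purpose) says the radiographic outcomes will be compared with a retrospective review. It reports that review's finding for plates kept at least 5 mm from the adjacent disc as "there was a decrease in the likelihood of moderate-to-severe adjacent-level ossification".

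**The concern.** The label and the grade list in Section 6 cannot both be applied. On the protocol's own scale, moderate-to-severe is Grade 2 or 3, whereas Grades 1 to 3 together are simply any ossification. Two analysts working from the same radiographs, one coding the label and the other the grade list, would report different values for the only primary endpoint.

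If the grade list is followed, mild cases are reported as moderate-to-severe and the headline proportion is set beside outside results described as excluding mild cases. That works against the device: performance equal to the earlier experience would look worse, and a real reduction could look like no difference.

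**Working it through.** **1. Inputs.** From Section 6: planning rate p = 0.455, half-width d = 0.10, two-sided α = 0.05 (z = 1.96), normal-approximation interval, 96 evaluable patients, 15% attrition. From Section 4.4.5: the meaning of each grade. Assumed, because the documents give no figure: m, the share of patients whose worst grade is Grade 1.

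**2. The plan's own sample size.**
- n = z² p(1 − p) / d² = 1.96² × 0.455 × 0.545 / 0.10² = 95.26, rounded up to 96.
- 96 / (1 − 0.15) = 112.94, rounded up to 113.

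Both stated figures reproduce.

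**3. Label against grade list.**

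| Grade | Meaning (4.4.5) | In a moderate-to-severe endpoint? | Counted by Section 6? |
|---|---|---|---|
| 0 | None | No | No |
| 1 | Mild | No | **Yes** |
| 2 | Moderate | Yes | Yes |
| 3 | Severe | Yes | Yes |

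The two definitions differ only in Grade 1, so reported rate = Grade 2–3 rate + m.

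**4. True Grade 2–3 rate equal to 45.5%, n = 96.** Interval: p ± 1.96 √(p(1 − p)/96).

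| Assumed m | Reported rate | 95% CI | Contains 45.5%? |
|---|---|---|---|
| 0 | 45.5% | 35.5% to 55.5% | Yes |
| 5 points | 50.5% | 40.5% to 60.5% | Yes |
| 10 points | 55.5% | 45.6% to 65.4% | No |
| 20 points | 65.5% | 56.0% to 75.0% | No |
| 30 points | 75.5% | 66.9% to 84.1% | No |

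A Grade 1 share of about 10 points, the same size as the planned half-width, is enough for the expected interval to exclude 45.5% through the definition alone.

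**5. True Grade 2–3 rate below the planning rate, n = 96.**
- Grade 2–3 at 25%: half-width 1.96 √(0.25 × 0.75/96) = 8.7 points, CI 16.3% to 33.7%, which lies below 45.5%.
- Add m = 20 points: reported 45%, half-width 1.96 √(0.45 × 0.55/96) = 10.0 points, CI 35.0% to 55.0%, which contains 45.5%.

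**6. Effect on sample size.** At p = 0.5, the least favourable value, n = 96.04 and the half-width with 96 patients is 10.0 points. At any other rate the half-width is smaller. The choice of definition therefore does not disturb 96 or 113.

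**The case against.** The contradiction shows that one half of the sentence is wrong, but not which half. Section 1 ends by speaking of adjacent-level ossification without a grade, Section 2 does the same, and Section 4.3 records heterotopic bone as present or absent. An any-grade endpoint with a wrong label is therefore possible. Whether the 45.5% really excludes mild cases depends on a cited study that cannot be checked here. This point stands as a condition on the fix. The text still leans clearly one way: moderate-to-severe is used for the objective, the precision target, the planning rate and the earlier review, while the conflicting grade list appears once. The same section also describes the estimated proportion as one of soft tissue masses, which suggests weak proofreading.

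The plan has no formal test against 45.5%. That figure is a planning rate, and the review named for comparison in Section 1 is a different citation from its source. This is correct, and the intervals above show how a reader would see the result, not a planned test. The 45.5% also applies to patients with a plate-to-disc distance above 5 mm, whereas the trial endpoint covers all patients, so correcting the grades would not by itself make the two fully comparable.

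The Grade 1 share is assumed, and the 25% plus 20 points example was chosen to land near the planning rate. Only the direction and the identity in step 3 are independent of that assumption.

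Finally, the four grades are recorded separately, so a Grade 2–3 proportion can be derived later. That keeps the repair cheap, but choosing between definitions once the 24-month results are known could look results-driven.

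**Conclusion.** The concern holds. As written, Section 6 counts every mild case as moderate-to-severe, and nothing elsewhere in the protocol, including the change history, resolves the conflict. The upward shift equals the proportion of patients whose worst grade is Grade 1. Under an assumed share of 10 to 30 points, that is one to three times the planned 10-point precision. The direction, against the device, rests on the protocol's own description of the outside rates as moderate-to-severe. If the 45.5% proved to be an any-grade rate, the label would be the error instead, and Section 6 would still need correcting. The fault lies in what is being estimated and what it can be compared with, not in the sample size. Because it affects the sole primary endpoint, it must be corrected before the 24-month radiographs are analysed.

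**What to change.** Confirm which grades the 45.5% covers in its source. Then amend Section 6 so that the primary endpoint is Grade 2 or 3 at any level on the 24-month lateral radiograph, which is the reading the protocol favours and which agrees with Section 4.4.5. Report any ossification (Grades 1 to 3) and the full distribution over Grades 0 to 3 as secondary descriptive results. Correct the formula legend in the same amendment so that the estimated proportion refers to this endpoint.

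The cost is a short protocol amendment. No new data are needed, since every grade is already recorded, and the targets of 96 evaluable and 113 enrolled stand.

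### The primary 95% interval is fixed as the Wald interval: adequate at the planned 45.5% and down to about 15%, but it under-covers if the ossification rate proves low, and a Wilson interval would avoid this at no cost

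*Combined protocol and SAP*

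**What the plan says.** Section 6 (Primary Objective and Sample Size Justification) sets one primary estimate: the proportion of patients with adjacent-level ossification at 24 months, "indicated by a severity of Grade 1, 2, or 3 at any level on the 24-month lateral radiograph". The inference is a single interval: "A point estimate and two-sided, 95% confidence interval for this endpoint will be calculated using the normal approximation to the binomial". The printed formula is the Wald interval with α = 0.05. No exact or score interval is named, and nothing is said about few or no events.

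The sample size rests on the same formula. The aim is to estimate, "within a precision of 10%, a 95% confidence interval for the proportion of patients with moderate-to-severe adjacent-level ossification". The rate assumed comes from a published series, where the figure "for patients with a PDD of > 5mm is 45.5"%. On that basis "a sample size of 96 patients will allow a precision of 10% to be achieved", and "Accounting for possible attrition of up to 15% gives a sample size of 113 patients".

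Section 1 (Study Purpose) says the technique allows placement 5 mm from the level above, "which will help minimize the risk of adjacent level ossification". It gives no target rate.

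**The concern.** The study is single-arm and its primary aim is estimation, so this interval is the whole of the primary inference. The Wald interval takes its width from the observed proportion. When that proportion is small, the estimated standard error is too small and the interval is too short and too close to zero. The errors then fall mainly on one side, with ossification reported as rarer than it is. In a sponsor-run study of a plate described as helping to limit ossification, that direction flatters the device.

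The planning rate is an assumption and the observed rate may differ from it. A prespecified interval should hold at whatever rate is seen. Changing the method after seeing few events would be a post hoc choice on the primary result.

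**Working it through.** **Inputs.** From Section 6: p = 0.455, half-width d = 0.10, two-sided 95% (z = 1.96), 96 evaluable patients, 15% attrition, 113 in total. From Section 3: enrolment up to 200. Every rate below 45.5% is an assumption, shown as a range.

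**The plan's own figures.** n = z²p(1 − p)/d² = 1.96² × 0.455 × 0.545 / 0.10² = 95.26, rounded up to 96. The half-width at n = 96 is 1.96 × √(0.455 × 0.545 / 96) = 9.96 points. With attrition, 96 / 0.85 = 112.9, so 113. Both figures reproduce.

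**Intervals compared.**
- Wald: p̂ ± z√(p̂(1 − p̂)/n).
- Wilson: [p̂ + z²/(2n) ± z√(p̂(1 − p̂)/n + z²/(4n²))] / (1 + z²/n).

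Exact coverage at a true rate p is the sum of binomial probabilities over all counts x whose interval contains p.

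**Coverage, Wald / Wilson (%), n = 96.**

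| True rate | Wald | Wilson |
|---|---|---|
| 45.5% (planned) | 94.9 | 94.9 |
| 40% | 95.1 | 95.2 |
| 30% | 95.4 | 95.5 |
| 25% | 95.1 | 95.6 |
| 20% | 94.1 | 94.5 |
| 15% | 94.7 | 95.6 |
| 10% | 91.3 | 96.1 |
| 5% | 85.6 | 94.2 |
| 2% | 85.3 | 95.6 |

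From 15% to 45.5% the two differ by less than one point at every rate checked.

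**Other sample sizes, Wald / Wilson (%).** At n = 113: 93.4 / 94.3 at 10%, 92.1 / 95.3 at 5%, 89.6 / 97.4 at 2%. At the enrolment ceiling of 200 less 15% attrition (200 × 0.85 = 170), Wald covers 94.8% at 10%, 91.9% at 5% and 85.3% at 2%.

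**Direction of the misses, n = 96.** Take a true rate of 5%. The Wald upper limit is 4.94% at x = 2 and 6.61% at x = 3, so the whole interval lies below 5% whenever x ≤ 2. P(X ≤ 2) = 13.58%. Misses on the other side have probability 0.86%, so coverage is 100 − 13.58 − 0.86 = 85.56%. The probability that the interval lies wholly below the truth (nominally 2.5%), Wald against Wilson, is 3.8% against 2.0% at a rate of 20%, 7.3% against 1.1% at 10%, and 13.6% against 0.7% at 5%. Wilson's misses at 5% lean the other way (100 − 94.2 − 0.7 = 5.1% lie wholly above), but its total stays near nominal.

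**Intervals at particular counts, n = 96.**

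| Events | Wald (%) | Wilson (%) |
|---|---|---|
| 0 | 0.0 to 0.0 | 0.0 to 3.85 |
| 1 | −1.0 to 3.1 | 0.2 to 5.7 |
| 3 | −0.4 to 6.6 | 1.1 to 8.8 |
| 5 | 0.8 to 9.7 | 2.2 to 11.6 |
| 10 | 4.3 to 16.5 | 5.8 to 18.1 |
| 44 | 35.9 to 55.8 | 36.2 to 55.8 |

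**Effect on the design.** At 44/96, the count nearest 45.5% of 96 (43.7), the half-width is 9.97 points for Wald, 9.77 for Wilson and 10.35 for Clopper-Pearson. For 10 points at 45.5%, Wilson needs 92 evaluable patients and Clopper-Pearson 103, against 96 for Wald.

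**The case against.** The strongest reply is that the Wald interval suits the plan as written. It matches the sample-size formula, and at the only rate the documents state it is as good as Wilson. The rate would have to fall below about a third of the planning value (45.5 / 3 = 15.2%) before the choice mattered. The 85.6% at a rate of 5% is partly a discreteness dip at n = 96, since the figure at n = 113 is 92.1%. The zero-width and negative intervals need 0 to 3 events, when about 44 are expected. The study is descriptive, with no hypothesis test, performance goal or threshold that turns on a confidence limit. All of this stands, and it sets the size of the point.

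A reader of Section 1 might go further and infer that a low rate is what the technique should deliver, so that the interval would fail just when the study succeeds. The documents do not support that. The 45.5% in Section 6 is the rate for a plate-to-disc distance above 5 mm, which is the placement that Sections 1 and 4.2 describe the technique as enabling. It is therefore the plan's expectation with the technique working as intended. Section 1 speaks of helping to limit the risk and sets no target. The Section 6 endpoint also counts Grade 1, labelled mild in Section 4.4.5, and counts it at any level. Both features can only raise the measured proportion.

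The reply does not show any advantage of Wald over Wilson at the planned rate, nor any provision for a low count if one occurs. Section 6 itself presents 45.5% as an assumption. If the event definition were reconciled to Grades 2 and 3 only, the proportion could only stay the same or fall.

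**Conclusion.** The point holds as a minor robustness correction to the primary analysis. At n = 96 the Wald interval is adequate at 45.5% and at the rates checked down to 15%. At about 10% and below it under-covers, by roughly 4 points at 10% (95 − 91.3 = 3.7) and 9 to 10 points at 5% and 2% (95 − 85.6 = 9.4; 95 − 85.3 = 9.7). At n = 113 the shortfalls are 1.6, 2.9 and 5.4 points. The misses mostly understate ossification.

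These losses depend on low rates that the documents neither state nor predict, so the finding is conditional: if the rate proves low, the prescribed interval will perform poorly. It is not a finding that the planned analysis fails at the design rate, or that the sample size is wrong.

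**What to change.** In Section 6, replace the normal-approximation sentence and formula with the Wilson score 95% interval for the primary proportion. Keep 96 evaluable and 113 in total, since the 10% precision is still met at 45.5%. Confine the change to the primary proportion, because no interval is planned for any other.

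The cost is one sentence and one formula, with no extra patients or data. The formula's legend needs an edit in any case, as it describes p̂ as a proportion of soft tissue masses, which is not this endpoint. Both changes can be made together.
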